# 2.6 Description of/and Justification for the Route of Administration, Dosage regime and Treatment period

The human complement C5 standing pool is about 200 mg in a 70-kg individual (amount of C5 protein that is maintained at a steady state by the liver and macrophages in a healthy person), assuming 2.8L serum and a C5 concentration of 70  $\mu$ g/ml serum. Given the (MW) of C5 (196kDa), the MW of Coversin (16.8kDa) and the fact that one molecule of Coversin binds one molecule of C5, it would be expected that 1mg of Coversin would bind 11.7 mg of C5. However, in the Phase Ia single ascending dose (SAD) study, which measured the concentration of C5 in the serum of individual healthy volunteers of known weight, it was shown that approximately a 1.8:1 molar excess of Coversin was necessary to completely inhibit C5 activation [Barratt-Due et al, 2011]. This means that it would take approximately 31.0 mg of Coversin to completely neutralise the standing pool of C5 in a 70-kg human. In the Phase Ia study, Cohort 4 subjects showed complete complement inhibition when administered 0.57 mg/kg Coversin. The heaviest patient in Cohort 4 that received Coversin weighed 93.6 kg and therefore was given a single total dose of 53.4 mg Coversin.

Pharmacokinetic studies in rats have shown that unbound Coversin is rapidly excreted by the renal route and that the serum half-life is ~30 minutes, whereas Coversin complexed with C5 has a circulating half-life of ~30 hours in rats [Hepburn et al, 2007]. The rate of production of C5 by humans is not known precisely. Sissons *et al.* using the Fick Principle and intravenously injected I labelled C5, calculated a daily turnover in normal humans of between 71 and 134  $\mu$ g/kg/hr (mean 90  $\mu$ g/kg/hr) [Sissons et al, 1977]. It is considered that turnover in autoimmune disease is not substantially different to that in normal patients. On this basis, the mean amount of C5 produced daily is roughly 151.2 mg and, using the calculation above it would take roughly 23.0 mg of Coversin to completely ablate it.

These figures indicate that a minimal loading ablation dose for a human is approximately 0.44 mg/kg (calculation 31 mg/70 kg) and minimal maintenance dose is approximately 0.018 mg/kg/hr (calculation 23.0 mg/24h).

Single i.v and 5-day s.c. dose toxicology studies in rats and cynomolgus monkeys were undertaken at doses up to 28.5 mg/kg. On a weight basis, this is 16 times more than the highest dose

administered to humans in a single day, which is 90 mg during the ablating phase equating to 1.8mg/kg in the lightest 50kg subjects.

Once daily repeat dose toxicology studies in mice (1-, 3- and 6-months) and cynomolgus monkey (1-month) have been performed using doses of up to 6.5 mg/kg (mouse, 6 months) and 4.8mg/kg (monkey, 1 month). On a weight basis, this is 7.2 times (mice) and 5 times (monkeys) more Coversin than the human maintenance dose of 45 mg QD administered to the lightest (50kg) patients which equates to 0.9mg/kg. To determine actual exposure to Coversin, empirical data on free drug levels and terminal complement activity in the cynomolgus monkeys dosed at 4.8mg/kg QD for 28 days was used re-parameterise the human PK/PD model for Coversin permitting an estimate of free Coversin  $C_{max}$ ,  $T_{max}$ ,  $C_{min}$  and AUC. Comparison of these values with the same values derived from humans under the dosing regimen proposed for AK580 CAPSTONE and this study showed that  $C_{max}$  and AUC of free Coversin are similar, and thus the 1-month toxicology findings in NHP provide a valid reference for anticipated safety in humans (Table 7). It was not possible to derive exposure data from the long-term mouse toxicology studies because blood samples were not taken at sufficiently short intervals after dosing.

PK Parameter	NHP a	Human b	Safety factor c
C max,ss	267.4	317.1	0.843
	(236.0 to 302.5)	(265.8 to 370.1)	(0.685 to 1.03)
Ctrough,ss	49.56	30.06	1.649
	(38.30 to 61.47)	(24.65 to 36.92)	(1.13 to 2.21)
AUC ss(0-24)	3185	3332	0.956
	(2743 to 3656)	(2949 to 3721)	(0.793 to 1.16)
T max,ss	0.326	0.918	0.355
	(0.310 to 0.344)	(0.831 to 1.011)	(0.317 to 0.396)

#### Table 7Safety Factor Calculation

However, Akari recognise that this exposure data is important and Akari are currently undertaking a study in same strain of mice as used for the long-term mouse toxicology studies to evaluate PK/PD. The expectation from these studies is that mice dosed s.c. at 6.6 mg/kg will have a very high  $C_{max}$  due to rapid absorption and relatively small AUC due to rapid elimination of unbound Coversin by mice. When available, these data will be presented in the Investigator Brochure.

In rat, mouse and cynomolgus monkey studies no drug related affects were detected other than for the 3- and 6-month mouse studies where there was an increase in the incidence and severity of microscopic signs of inflammation detected by histopathology at the site of injection (scapular region only in mice) which were considered related to Coversin. In the 6-month mouse study minor immunostimulation in local lymph nodes in both sexes was observed in the highest dose group (6.5 mg/kg) and in the spleen of treated males. In the 6-month mouse and 1-month NHP study the NOAEL was determined to be 6.5 mg/kg and 4.8 mg/kg respectively.

The Phase I SAD study (VA576) maximum activity was seen between 6 and 12 hours after injection. Recovery due to gradual replenishment of C5 by the liver and other tissues was such that at 96 hr post-dose, CH50 had only returned to approximately 75% of baseline. At the time this result was obtained, it was unexpected since onset of action was faster and duration of action shorter in animals, including cynomolgus monkeys, than in humans. Subsequent empirical data

and PK/PD modelling of the dynamics of Coversin in cynomolgus monkey and man, indicate that the absorption rate from the s.c. site of administration in monkeys and man is equivalent but that the smaller intravascular volume and higher relative clearance rate of Coversin result in more rapid onset and offset of action in monkeys than in man.

In the Phase Ib study (AK577) in all placebo-treated subjects, CH50 results remained at around baseline levels throughout the dosing period. In contrast, the Coversin AD fully inhibited complement activity. CH50 results were inhibited by >90% from 24 h after the start of the AD period until the end of the AD period (i.e. the morning of Day 3). During maintenance dosing with 15 mg Coversin, once daily, for 5 days, complement activity remained low, but not fully inhibited (Figure 4). During maintenance dosing with 22.5 and 30 mg Coversin, once daily, for 5 days, complement activity remained almost completely inhibited. For the maintenance dose of 22.5 mg Coversin, all 4 subjects had CH50 values up to about 10% of baseline at 24 h after the final maintenance dose of Coversin (Figure 4). Thus, 22.5 mg Coversin, once daily, was selected as an effective dose that could minimise Coversin exposure. To further explore this effective dose, a longer dosing period was tested in Cohort 4, in which all patients received a maintenance dose of 22.5 mg Coversin for 19 days. In all 4 patients, complement activity was almost completely inhibited throughout the maintenance dosing period and for the 24 h after the final maintenance dose (Figure 4). Recovery to baseline complement activity took approximately 5 days.

Pharmacokinetic/pharmacodynamics (PK/PD) data obtained from healthy volunteers and patients in the Phase II study (AK579) has been used to develop a kinetic model to more fully understand the dynamics of the Coversin-complement C5 system in relation to dosing and individual variation between subjects. As briefly described below (and more fully in the IB) the PK/PD modelling analysis supports increasing the fixed initiation and maintenance doses of Coversin to 22.5 mg and 45 mg for treatment of PNH.

At steady state Coversin administered subcutaneously enters the circulation relatively rapidly with free Coversin levels peaking between 1 to 3 hours after administration depending on the dose. The level of free Coversin then declines over 24 hours to Cmin immediately prior to the next dose. The Cmin value determines the degree of residual complement inhibition 24 hours after the last dose by determining the proportion of C5 that is bound by Coversin which therefore cannot be activated by the alternative and classical/lectin C5 convertases. For the first 5 PNH patients admitted to AK579 by PK/PD modelling the mean values  $\pm$  SD for Cmax, Tmax and Cmin were estimated. During the ablating phase  $C_{max}$  was  $164.5 \pm 46.8 \ \mu g/L$ ,  $T_{max} = 0.93 \pm 0.43h$  and  $C_{min} = 87.5 \pm 25.3 \ \mu g/L$ . with a dose of 22.5 bid, During the initiation phase mg Cmax was  $138.8 \pm 69.2 \ \mu g/L$ ,  $T_{max} = 1.03 \pm 0.28h$  and  $C_{min} = 87.1 \pm 66.0 \ \mu g/L$ . During the maintenance phase at a dose of 45 mg once daily the  $C_{max}$  was  $160.7 \pm 75.6 \ \mu g/L$ ,  $T_{max} = 1.24 \pm 0.34h$  and  $C_{min} = 65.5$  $\pm$  58.4 µg/L.

Coversin has a short half-life when it is not bound to C5, estimated at approximately 1h in man, whereas the half-life of Coversin bound to C5 is estimated to be equivalent to the half-life of unbound C5 which has a reported average of 63 hours in man [Sissons et al, 1977]. When considering the Coversin dosing regimen a critical value is the lowest concentration of free rVA576 that inhibits terminal complement activation by 95%. Both simulation PK/PD modelling and theoretical estimates put this value at 20  $\mu$ g/L. To maintain control of complement this value must be exceeded at Cmin i.e. immediately before receiving the next dose. As illustrated in the

preceding paragraph the dosing regimen proposed for initiation and maintenance dosing exceed 20  $\mu\text{g/L}.$ 

A second consideration in selection of dose is to ensure that the concentration of Coversin stays above 20  $\mu$ g/L even when the drug is not administered at exactly the same time each day. This is more likely to fall below 20  $\mu$ g/L on maintenance dosing than on initiation dosing. The PK/PD model was used to undertake a simulation to determine the elapsed time from the last QD dose until free C5 exceeds 5% (this is equivalent to terminal complement activity of 5%). For 45 mg QD maintenance dosing the median time is 26.5 hours, with interquartile ranges of 25.5 and 31. The median is preferred to the arithmetic mean because the time from dose until free C5>5%, like many PK-related parameters, is log normally distributed. This on 45 mg QD the majority of patients have a window of a few hours each day in which to dose themselves to maintain complement activity below the limit of quantification (i.e. <8 CH50 U Eq/mL).

A third consideration which has informed our proposed fixed dosing regimen for Phase III is interindividual variation in subjects' initial C5 concentrations and CH50 values. The PK/PD model was used to simulate 1000 patients. Covariate values for initial C5 concentrations and CH50 values were sampled from log-normal distributions with parameters set to sample estimates calculated from the data observed in patients and healthy volunteers to date. The analyses showed that terminal complement activation is more completely controlled in a higher proportion of patients on 22.5 mg q.12h than15 mg q.12h dosing, and on 45 mg QD than 30 mg QD dosing. For example, the percentage of the simulated patient population with free C5 < 5% of baseline at Coversin trough is 80.7% on 45 mg QD and 58.1% on 30 mg QD.

In the AK579 Phase II trial rVA576 has proven safe and well tolerated at 22.5 mg q.12h and 45 mg QD, and these doses will provide near complete control of terminal complement activation in most patients therefore our proposed fixed dosing regimen for AK585 is 60 mg start dose followed by 30 mg 12h later to ablate complement, then 22.5 mg q.12h for 27 days initiating dose, and 45 mg QD maintenance dosing for the rest of the trial.

Coversin is administered by patients subcutaneously and the proposed dosing regimen as stated above is an initially 60 mg dose followed by 30 mg 12 hours later, then 22.5 mg q.12 hourly up to Day 28 and then 45 mg once daily for the remainder of the study or patients may be switched back to 22.5 mg q.12 hourly if not fully responding. This dosing schedule has been based on the initial data from the Phase Ib (AK577) and Phase II AK579 study and the data from the first five patients and also on the PK modelling data provided above. This dosing schedule has been successfully trialled in 3 patients so far and has been followed by all three patients with no deviations. It was found that the expected doses that had shown an effect in health volunteers did not quite provide the same effect in patients with patients needing slightly higher doses.

# **3 TRIAL OBJECTIVES AND ENDPOINTS**

# 3.1 Trial Objectives

The trial objectives of this study are to demonstrate the safety and efficacy of Coversin when given to patients with PNH and known resistance to eculizumab (*Soliris*®).

- 1) To assess the safety and tolerability of Coversin for patients between 50 and 100kg (110lb -220lb) body weight when given as a fixed maintenance dose following an initial AD and Initiation Phase.
- 2) To assess whether this dosage regimen is sufficient to control the signs and symptoms of PNH (see Endpoints).

## 3.2 Endpoints

Primary Efficacy Endpoint:

• Reduction in serum LDH from baseline to mean of Day 43, 60, 90, 120, 150 and 180

Secondary Efficacy Endpoints:

- Change in LDH from baseline at monthly intervals after Day 28, 60, 90, 120, 150 and 180
- Change in mean Hb: baseline Day 180
- Change in FACIT score: baseline Day 28 Day 180
- Change in EQ-5D-5L QLQ C30 score: baseline Day 28 Day 180
- Number of transfusions: baseline to Day 180

Safety Endpoints:

- Frequency, type and relationship of AEs and SAEs to treatment
- Out of range laboratory parameters (hematology and chemistry)
- Vital signs (blood pressure, body temperature and pulse rate)
- ECG abnormalities baseline Day 180 (A resting pre-dose ECG taken within 7 days of first dose will be compared with ECGs taken 1- 6 hours post-dose and at 180 days of treatment with Coversin)
- Change in weight will be noted baseline and at Day 180
- Injection site reaction and lymph node inspection
- Anti-Coversin antibody production

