	will allow adequ	Ideally, all patients will be on a stable dose by Day 150 of the trial. This will allow adequate time to confirm that this dose is satisfactory for long-term treatment under the long-term safety trial or to ensure that						

	arrangements can be put in place to allow the patient to be switched to alternative treatment with no interruption of treatment.				
	Inadequate Response				
	Existing Switch to				
	DoseIntervalDoseInterval22.5 mg12 hourlyWithdraw patient				
	45 mg24 hourly22.5 mg12 hourly				
Duration of	180 days				
Treatment:	Patients completing 180 days of treatment will have the option of enterin an additional long-term safety trial at the discretion of their PI at Day 18 The long-term safety trial will continue until approval of Coversin.				
Endpoints:	Efficacy Endpoints				
	Primary:				
	Reduction in serum LDH from baseline to mean of Day 43, 60, 90, 120, 150 and 180				
	
 
Secondary:
 
Change in LDH from baseline at monthly intervals after Day 28, 60, 90, 120, 150 and 180
 
				
	• Change in mean Hb from baseline – Day 180				
	
 
Change in Functional Assessment of Chronic Illness Therapy (FACIT) score baseline – Day 28 - Day 180
 
				
	
 
Change in EuroQol 5 dimensional 5 level (EQ-5D-5L) score from baseline – Day 28 - Day 180
 
				
	• Number of transfusions from baseline to Day 180				
	Safety Endpoints:				
	• Frequency, type and relationship of AEs and SAEs to treatment				
	• Out of range laboratory parameters (hematology and chemistry)				
	• Vital signs (blood pressure, body temperature and pulse rate)				
	• Electrocardiogram (ECG) abnormalities baseline – Day 180 (A resting pre-dose ECG taken within 7 days of first dose will be compared with ECGs taken 1- 6 hours post-dose and at 180 days of treatment with Coversin)				

	• Change in weight will be noted baseline and at Day 180
	• Injection site reaction and lymph node inspection
	Anti-Coversin antibody production
Statistical	Descriptive statistics
Methods:	

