## **5 TRIAL DESIGN AND PROCEDURES**

## 5.1 Trial Design

The trial is a 180-day open-label, non-comparative study in up to 6 patients with PNH who have received eculizumab (*Soliris*®) without apparent benefit and in whom it has been demonstrated that their serum is resistant to eculizumab (*Soliris*®) at any concentration but sensitive to Coversin using a CH50 assay. They should also have the presence of a C5 polymorphism confirmed by genetic testing, but treatment need not be delayed until these results are available, since the results of the CH50 spiking assay are sufficiently sensitive to identify patients who are resistant to eculizumab (*Soliris*®), but sensitive to Coversin and genetic testing may take up to 8 weeks. Patients must also meet the inclusion and exclusion criteria.

Treatment Dose/Phase Day		Dose	
A 1-1-4:	D 1	60 mg (between 7am -11am)*	
Ablation	Day 1	30 mg (between 7pm -11pm)*	
	D 2 D 20	22.5 mg (between 7am-11am)*	
Initiation	Day 2 – Day 28	22.5 mg (between 7pm-11pm)*	
MaintenanceDay 29 – Day 18045 mg (between 7am-11am)*		45 mg (between 7am-11am)*	

Table 8	Treatment Regime
---------	-------------------------

\*Patients to select a set time for dosing (eg., 7am and 7pm) and administer dose within 1 hour either dose of set time(s).

The trial will last 180 days in total for all patients, although the exact length of each phase will be adjusted to ensure that optimal laboratory and clinical support is available during the change from q. 12 hourly to q. 24 hourly dosing.

The dosing regimen is designed to be flat (fixed dose) for all patients between 50 and 100kg (110 lb -220 lb) in weight. The obvious advantage of this is that, since it is intended that patients will self-inject Coversin, it simplifies the drawing up and administration of the drug and reduces the possibility of error. All patients treated under this protocol will be given adequate support to ensure that they are able to draw up and self-administer Coversin accurately and safely.

The alternative, that of individualizing doses to the patient's weight, makes calculating and drawing up doses complicated and subject to error if the patient's weight varies during the course

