## **12 STATISTICS**

## **12.1 Statistical Methods**

The statistical approach taken will depend on the number of patients recruited.

If less than 4 patients are recruited, each patient will be analyzed separately and no formal statistical analysis plan will be written. Changes in the primary efficacy outcome during the period baseline to mean of Day 43, 60, 90, 120, 150 and 180 will be analyzed using linear regression using all measurements in the analysis. Secondary efficacy outcomes measured multiple times will be analyzed in an equivalent manner.

If 4 or more patients are recruited, the patients will be analyzed as a single group. Differences between specific time points (e.g. baseline and mean of Day 43, 60, 90, 120, 150 and 180) for the primary and secondary efficacy endpoints will be performed using the paired t-test.

Additionally, the change in the primary efficacy outcome over time will also be examined using all measurements. Mixed model will be used to allow for repeat measurements from the same patients, with the patient considered as a random effect.

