## **12.2** Number of Patients

A total of up to 6 patients may be enrolled under this Protocol.

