## 12.3 Significance Level

All significance tests will be purely descriptive.

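### The transfusion endpoint is a bare on-study count with no pre-treatment count and no time at risk, so it cannot show a change in transfusion need and its summary depends on length of follow-up

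*Combined protocol and SAP*

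**What the plan says.** The body of the protocol defines the endpoint as "Number of transfusions: baseline to Day 180" (Section 3.2), and the synopsis as "Number of transfusions from baseline to Day 180". Neither gives a unit (episodes or red-cell units), a look-back period or a rate. The other secondary efficacy endpoints are worded as changes, for example "Change in mean Hb: baseline Day 180".

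Section 5.1 describes the design: "The trial is a 180-day open-label, non-comparative study in up to 6 patients with PNH".

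For four or more patients, Section 12.1 says that differences between time points "for the primary and secondary efficacy endpoints will be performed using the paired t-test". For fewer than four, each patient is analysed separately, the primary outcome by linear regression, and "Secondary efficacy outcomes measured multiple times will be analyzed in an equivalent manner". Section 12.3 adds: "All significance tests will be purely descriptive".

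Three other parts of the protocol bear on how long a patient is counted and who is analysed:

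- **Withdrawal.** Section 6.1 withdraws as treatment failures those whose response is still inadequate three weeks after the daily dose is divided. Section 5.2 allows withdrawal for poor response to be considered as early as the Initiation Phase.
- **Follow-up after stopping.** Sections 5.3 and 6.3 provide 30 days (Section 5.3 as a minimum), not follow-up to Day 180.
- **Analysis set.** Section 12.6 names an intention-to-treat primary analysis. It also limits each time-point analysis to patients who get that far, and limits efficacy data to periods when the protocol was correctly followed.

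**The concern.** The second trial objective (Section 3.1) is to judge, through the endpoints, whether the regimen controls the signs and symptoms of PNH. Without a control arm, the only comparator for transfusions is the patient's own history. Appendix 1 lists medical history by body system, with no transfusion item and no look-back. The schedule of events has no transfusion row. A total collected only on study therefore has nothing to be judged against.

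A total also grows with time observed, and this protocol ends observation sooner in patients who respond poorly. With at most six patients, one or two early exits can move the group summary noticeably. The reader of the final report could not separate fewer transfusions from fewer days, or from the loss of failures from the analysis.

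**Working it through.** The plan states no transfusion rate, expected count or power figure, so there is nothing of its own to reproduce. Every rate and withdrawal pattern below is an assumption.

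**Inputs from the documents**

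- Patients: up to 6 (Section 12.2).
- Treatment period: 180 days (Section 5.1).
- Maintenance dose change allowed after Day 36 (Section 5.3). Failure is declared 3 weeks later (Section 6.1), so a maintenance-phase failure can leave at about Day 36 + 21 = 57.

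**Assumptions**

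- Constant rate r of 0.5, 1 or 2 transfusions per 30 days, with no drug effect.
- 1 to 3 withdrawals, at Day 28, 57, 60, 90 or 120.

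**Step 1: can the count show change?** Change = on-study count − prior 180-day count. For an on-study count of 6:

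- prior count 2: 6 − 2 = +4 (a rise);
- prior count 6: 6 − 6 = 0 (no change);
- prior count 12: 6 − 12 = −6 (a fall).

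The same observed value fits all three, and the plan does not collect the number that would decide.

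**Step 2: which stated analysis applies?** With four or more patients, a paired test needs two values per patient; a total that starts at baseline supplies one. With fewer than four, regression is extended only to outcomes measured repeatedly, and a single total is not one.

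**Step 3: one patient, all counts kept.** Expected count = r × d/30 for d days observed. Relative to 180 days this is d/180, whatever r is.

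| Last day | d/180 | Shortfall | Expected count at r = 1 |
|---|---|---|---|
| 28 | 0.156 | 84% | 0.93 |
| 57 | 0.317 | 68% | 1.90 |
| 60 | 0.333 | 67% | 2.00 |
| 90 | 0.500 | 50% | 3.00 |
| 120 | 0.667 | 33% | 4.00 |
| 180 | 1.000 | 0% | 6.00 |

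**Step 4: group of six, all counts kept.** Shortfall in the mean = (k/6) × (1 − d/180) for k withdrawals.

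- Day 57: 11%, 23% and 34% for k = 1, 2 and 3.
- Day 28: 14%, 28% and 42%.

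**Step 5: only patients reaching Day 180.** The truncated counts leave the analysis, so the Step 3 mechanism does not operate. What matters is whether those who left had a different rate.

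- Everyone at 1 per 30 days: the completer mean is 6.0, the same as if all six were followed. There is no distortion.
- Four completers at 0.5 and two failures at 2 per 30 days: the completer mean is 3.0. With all six followed it would be (4 × 3 + 2 × 12)/6 = 6.0. Keeping the failures' counts truncated at Day 57 gives (4 × 3 + 2 × 3.8)/6 = 3.27.

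**Step 6: with days as the denominator.** Count/days × 30 returns r in every constant-rate scenario, a ratio of 1.00 to the true rate. In the mixed example, the mean of the six patients' own rates is (4 × 0.5 + 2 × 2)/6 = 1.0 per 30 days, which equals 6.0 per 180 days. Pooling first gives 19.6/834 × 30 = 0.705, because the failures contribute fewer days. The rate should therefore be formed patient by patient.

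**The case against.** A reader might infer that early withdrawal will necessarily look like benefit under this plan, or that the plan would report a 67% reduction. The documents support neither. The 67% is 1 − 60/180 under an assumed constant rate; the plan computes no percentage reduction and collects no prior count from which to do so. Under the Section 12.6 rule on reaching the time point, a patient withdrawn at Day 60 is absent from a Day 180 analysis, so truncation has no effect there. Any distortion then comes from leaving out failures, and its direction depends on their transfusion rate. A higher rate in patients withdrawn for poor response is plausible, but the documents do not establish it.

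The t-test point can also be contested. Section 12.1 attaches the test to differences between time points, and this count is not worded as one. The synopsis gives descriptive statistics as the method, so the count may simply be meant for summary. That is a fair reading, but Section 12.1 does name the secondary endpoints without exception. If the test does not apply, the count has no stated method and still no comparator.

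Finally, the stakes are limited. This is one of five secondary endpoints, tests are descriptive, and with so few patients a withdrawal date can be read beside a count. General history and concomitant-medication records may hold some earlier transfusions, and the eCRF is not reproduced in the documents. These facts reduce the harm, but nothing in the text sets a look-back or says such records feed this endpoint.

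**Conclusion.** The point holds in two parts.

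- **No comparator.** This is certain from the text. The endpoint is an on-study total in a non-comparative trial, with no pre-treatment count. It cannot show a change in transfusion need, and a paired analysis has nothing to pair.
- **Dependence on follow-up.** This is conditional on how Section 12.6 is read. If all counts are kept, truncation lowers them: to one third for withdrawal at Day 60, and by 11% to 34% in the mean of six for one to three withdrawals at Day 57. Those sizes rest on a constant rate and assumed withdrawals; the downward direction of truncation does not depend on the rate chosen. If only patients reaching Day 180 count, the result favours the drug only if the failures were transfused more often than completers.

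No error rate or power is affected. This is an inexpensive improvement to a descriptive secondary endpoint, worth making because the present form cannot answer the question it is listed for.

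**What to change.** - **Collect a prior count.** From existing records, abstract transfusion episodes and red-cell units over a stated window before Day 1. A window of 180 days would match the treatment period, but its length is a choice; what matters is that it is fixed in advance.
- **Date on-study transfusions.** Add a transfusion row to the schedule of events, with date and units.
- **Redefine the endpoint.** For each treated patient, including those withdrawn, report the prior rate and the on-study rate (for example units per 30 days, using actual days observed), and the difference between them. Form the rate per patient before any averaging.
- **State the analysis.** Describe the within-patient change and give a per-patient listing with counts, days observed and reason for leaving. Say in Section 12.6 that withdrawn patients are included for this endpoint.

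The cost is abstraction for up to six patients, a few eCRF fields and one rate calculation. Some prior records may be incomplete, so the days actually covered should be recorded too. Rates from short windows are imprecise: at 1 per 30 days, a Poisson patient seen for 57 days has a 15% chance of no transfusion (exp(−1.9)), against 0.25% over 180 days (exp(−6)). The usual limits of a single-arm before-and-after comparison remain.
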